## 9.3. Populations for Analyses

The analysis sets are defined in Table 9.

Table 9: Study WTX101-HV-106 Analysis Sets

Population	Description	
Enrolled	All subjects who sign the ICF	
Safety Set	All subjects who receive at least 1 dose of study drug	
Pharmacokinetic	All subjects who have sufficient plasma samples to enable the calculation of PK	
	parameters	
Pharmacodynamic	All subjects who have sufficient plasma samples which will enable the	
	evaluation of the PD effects	

Abbreviations: ICF = informed consent form; PD = pharmacodynamic; PK = pharmacokinetic.

## 9.4. Statistical Analyses

In general, descriptive statistics for continuous variables will include number of nonmissing values, arithmetic mean, SD, median, minimum, and maximum. Descriptive statistics for PK parameters will include number of observations, arithmetic mean, SD, arithmetic coefficient of variation (%CV), median, minimum, maximum, geometric mean and geometric %CV. Categorical variables will be summarized using percentages and frequency counts. Descriptive statistics and percentages and frequency counts will be summarized by cohort, dose level, and time point, where appropriate.

All statistical analyses will be conducted using SAS® for Windows® Version 9.3 or higher.

A SAP will be developed and finalized before data cutoff/database lock and will further describe the subject populations to be included in the analyses, and procedures for accounting for missing, unused, and spurious data as appropriate. This section is a high-level summary of the planned statistical analyses of the primary and secondary endpoints.

## 9.4.1. Efficacy Analyses

No efficacy analyses will be performed for this study.

## 9.4.2. Safety Analyses

All safety analyses will be performed on the Safety Set.

Safety analyses will include an analysis of all AEs, ECGs, clinical laboratory data, physical examinations, and vital sign measurements using descriptive statistics. No inferential statistical analyses are planned on the safety parameters of this study. The incidence of AEs and SAEs will be summarized, by System Organ Class and Preferred Term for each cohort and overall, by relationship to study drug. Adverse events will also be summarized by cohort and overall by severity. Serious AEs and AEs resulting in withdrawal from the study will be listed. Subjects having multiple AEs within a category (eg, overall, System Organ Class, Preferred Term) will be counted once in that category. For severity tables, a subject's most severe event within a category will be counted.

Changes from baseline in vital sign measurements and laboratory assessments (eg, chemistry, cell blood count with differential, and urinalysis) will be summarized by Japanese and non-Japanese (cohort) and dose. CTCAE will be used as a guide to grade laboratory parameter values in conjunction with clinical judgement. Shift tables by cohort will be produced for these laboratory parameters. These tables will summarize the number of subjects with each baseline grade relative to the reference ranges and changes to the worst highest grade assessed post-dose during the study.

The ECG parameters will be measured at the specified time points, including heart rate, PR, RR, QRS, QT, and corrected QTcF intervals. The average of the triplicate ECG readings at the time points collected will be calculated, and changes from pretreatment baseline values will be assessed by each cohort.

All concomitant medications will be coded using the WHO Drug Dictionary, and the frequency and percentage of concomitant medications will be summarized.

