## **4. STATISTICAL ANALYSES**

In general, descriptive statistics for continuous variables will include number of non-missing values (n), arithmetic mean (Mean), standard deviation (SD), median, minimum, and maximum.

Descriptive statistics for PK parameters will include number of observations (n), arithmetic mean (Mean), standard deviation (SD), arithmetic coefficient of variation (%CV), geometric mean, geometric %CV, median, minimum and maximum.

Categorical variables will be summarized using frequency counts and percentages.

For all tables, except PK parameter tables, descriptive statistics for minimum and maximum will be presented with the same decimal digits as the original data, and with 1 more decimal place than the original data for mean and median; SD will be reported with 2 more decimal places than the original data.

PK parameters will be presented as follows in the listing:  $C_{max}$  and  $T_{max}$  will be presented as given in the raw data;  $AUC_t$ ,  $AUC_{\infty}$ ,  $\lambda_z$ ,  $t_{1/2}$ , CL or CL/F, and  $V_d$  or  $V_d/F$  will be presented with 3 decimal places. Special characters (including subscripts) will not be presented in the tables, listings or figures. Descriptive statistics for PK parameters will be presented with decimal places as appropriate for the particular parameter and cohort.

The analyses will be presented by cohort and period. All collected data will be presented in by-subject listings. Listings will be ordered by cohort, period and subject number and will include all randomized subjects. Deviations from this scheme, if any, will be specified in the relevant section.

Baseline will be defined as the last non-missing value among assessments recorded prior to administration of study drug within respective period. Changes from baseline values will be calculated by period as the post-baseline assessment value minus the baseline value. Only observed values from scheduled time points will be used to create summary tables.

Early Termination (ET) visits will be recoded to ET visits where necessary and reported as ET.

Deviations from the planned analyses will be described in the final clinical study report (CSR).

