## **4.4 Demographic Characteristics**

Individual subject demographics (including age, sex, race, ethnicity) and body measurement data (height, body weight and body mass index) at screening will be listed and summarized for each cohort and overall for the safety population. If

the remaining populations are different from the safety population by more than 5%, separate demographic tables will be produced.

For the Japanese cohort, information about the Japanese criteria information (descent, place of birth and residence) will be listed.

Height will be measured in centimeters and weight in kilograms. Body mass index will be given in kg/m^2.

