### **4.11.1 Adverse Events**

A Treatment Emergent Adverse Event (TEAE) is any adverse event that commences after the start of administration of study drug. TEAEs will further be classified by the Period in which they commenced. A TEAE will be classified as Period 1 if the AE start date/time is on or after the date and time of drug administration in Period 1, and Period 2 if the AE start date/time is on or after the date and time of drug administration in Period 2.

The incidence of TEAEs (after dosing) will be summarized using the safety population. The MedDRA dictionary Version 21.1 (or higher) will be used to classify all AEs reported during the study by System Organ Class (SOC) and Preferred Term. A summary of TEAEs including the incidence of subjects who experienced TEAEs (number and percentage of subjects) and incidence of TEAEs (number of events) will be presented for each cohort and overall, by severity and by relationship to study drug.

TEAEs and serious TEAEs will be summarized by SOC and Preferred Term for each cohort and overall, and by relationship to study drug.

Subjects having multiple AEs within a category (e.g., overall, SOC and Preferred Term) will be counted once in that category. For severity tables, a subject's most severe event within a category will be counted. For relationship tables, a subject's event with greatest relationship to study drug within a category will be counted.

All adverse events will be listed. Serious TEAEs and AEs resulting in withdrawal from the study will be listed.

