#### *4.11.4 Vital Signs*

Vital signs data (systolic and diastolic blood pressure, heart rate, temperature and respiration rate) will be listed for individual subjects. Summary statistics of absolute (observed) values and changes from baseline will be calculated for each parameter and scheduled time point by cohort and dosing regimen.

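### The TEAE tables name neither dose nor period, and the Period 1 TEAE window has no end, so the SAP does not settle whether events at 15 mg and 60 mg are shown apart.

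*Protocol*

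**What the plan says.** **AE tables.** Under protocol section 9.4.2, AE and SAE incidence "will be summarized, by System Organ Class and Preferred Term for each cohort and overall, by relationship to study drug". For severity, "Adverse events will also be summarized by cohort and overall by severity". A subject with several AEs in a category "will be counted once in that category", and the severity tables use that subject's worst event. SAP section 4.11.1 follows suit: "TEAEs and serious TEAEs will be summarized by SOC and Preferred Term for each cohort and overall, and by relationship to study drug". Its TEAE overview is also laid out by cohort and overall, by severity and relationship. The once-per-subject and worst-grade rules are repeated there without saying whether they apply within a period or across the study.

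**Other safety outputs.** In protocol section 9.4.2, changes in vital signs and laboratory values "will be summarized by Japanese and non-Japanese (cohort) and dose". In the SAP, laboratory summaries and shift tables (4.11.2) and ECG summaries (4.11.3) name cohort and period. Vital signs (4.11.4) are summarised "for each parameter and scheduled time point by cohort and dosing regimen".

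**General defaults.** Protocol section 9.4 has counts and percentages broken down by cohort and dose level where that is appropriate. SAP section 4 makes cohort and period the default presentation, then adds: "Deviations from this scheme, if any, will be specified in the relevant section".

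**Period of onset.** SAP section 4.11.1 assigns each TEAE to a period. Period 1 covers any start at or after the Period 1 dose. Period 2 covers any start at or after the Period 2 dose. No upper limit is given for Period 1.

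**The concern.** The study is meant to inform whether 15 to 60 mg is appropriate for Japanese patients in the Phase 3 study, and TEAE incidence is the first item of the secondary endpoint. The doses differ four-fold and are given to the same subjects in a fixed order, so a reader will want to see AE incidence and severity at each dose in each cohort. Tables built literally from the AE sentences would not show this. They would give one count per subject over both doses, at the worst grade over both doses.

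There is also a difficulty for whoever programs the tables. One programmer could apply the SAP section 4 default and split by period, and another could follow section 4.11.1 and pool. If the split is chosen, the Period 1 definition as written also takes in events that began after the 60 mg dose.

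**Working it through.** The plan gives no figure on this point to reproduce. The check is a comparison of the texts, followed by arithmetic on assumed counts. Planned enrolment of 12 per cohort, with at least 10 completing, comes from protocol section 9.2. The fixed order of 15 mg then 60 mg comes from protocol sections 1.2 and 4.1.

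**1. Which outputs name dose or period?**

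| Output | Protocol 9.4.2 | SAP |
|---|---|---|
| AE incidence by SOC/PT | cohort, overall | cohort, overall (4.11.1) |
| AE severity | cohort, overall | cohort, overall (4.11.1) |
| Laboratory changes | cohort, dose | cohort, period (4.11.2) |
| Laboratory shift tables | cohort | cohort, period (4.11.2) |
| ECG changes | cohort | cohort, period (4.11.3) |
| Vital-sign changes | cohort, dose | cohort, dosing regimen (4.11.4) |
| Concomitant medication | no split named | no period named (4.10) |

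The SAP added period to the shift tables and the ECG summaries, where the protocol had cohort only. It did not add it to the AE tables.

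**2. Do the defaults settle it?** The protocol default depends on a judgement of what is appropriate. The SAP default yields to the specific section, and 4.11.1 states its own layout. SAP section 4.4 uses the same phrase for demographics, which "will be listed and summarized for each cohort and overall for the safety population". Those are screening data with no period column, so this is weak support for reading the phrase as excluding period. Classifying each TEAE by period does not by itself commit the SAP to tabulating by period.

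**3. What a pooled table loses (assumed counts, 12 per cohort).**

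- Pattern A: 3 subjects have an event after 15 mg; the same 3 and 3 others have one after 60 mg. By dose: 3/12 = 25% and 6/12 = 50%. Pooled: 6/12 = 50%.
- Pattern B: 6 subjects have an event after 15 mg, none after 60 mg. By dose: 6/12 = 50% and 0/12 = 0%. Pooled: 6/12 = 50%.

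In general, if k subjects appear in the pooled row and a of them had an event at 15 mg, the 60 mg count lies anywhere from k − a to k. With k = 6, the difference (60 mg minus 15 mg) can be anything from −6 to +6 subjects, that is −50 to +50 percentage points.

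The same happens with severity. A subject at Grade 1 after 15 mg and Grade 2 after 60 mg appears once, at Grade 2, exactly like a subject with the grades reversed.

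**4. What the open Period 1 window does.** Take pattern A and apply the two definitions literally. All 6 subjects have an event starting at or after the Period 1 dose, so Period 1 shows 6/12 = 50% in place of 3/12 = 25%. Period 2 also shows 6/12 = 50%. The split table would then hide the rise that it was meant to show.

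**5. Denominator.** Protocol section 6.7 allows for subjects who do not receive the second dose. If 2 of 12 leave before Period 2 (an assumption, matching the 10 planned completers) and 6 have an event after 60 mg, the rate is 6/10 = 60% among those dosed, against 6/12 = 50% on the full cohort.

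**The case against.** The best case for the plan is that it already implies a split. AE incidence is a count and percentage, so the protocol section 9.4 rule on dose level covers it. The same passage calls the section a high-level summary. In the SAP, cohort and period is the default, and 4.11.1 never says that TEAEs are pooled; its reference to each cohort and overall can be read as adding an overall column. It also classifies TEAEs by period, which equals dose here. The table shells are a separate document that was not available and may show the split. Finally, all AEs are listed, ordered by cohort, period and subject, so with about 24 subjects a reader can recover events by dose.

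Much of this stands. It rules out two stronger readings that a reader might infer. The first is that the plan has definitely decided to pool; the defaults leave that open. The second is that AEs are the only safety output without a dose split. That is not so: ECG changes and shift tables in protocol section 9.4.2 are also by cohort alone, and the concomitant-medication summary in SAP section 4.10 names no period. The contrast holds only against the laboratory, ECG and vital-sign summaries in SAP section 4.11.

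The objection does not show that the text is clear. A listing is not an incidence table, and the period classification that it relies on is the one with the open window.

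It is also fair that the safety objective compares cohorts and not doses, that dose proportionality is a PK objective only, and that counts will be small. These points limit what a split can show. They are not reasons to leave it unspecified.

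**Conclusion.** The point holds as an unresolved ambiguity with a likely outcome. The AE table sentences in protocol section 9.4.2 and SAP section 4.11.1 name neither dose nor period. Taken literally, they pool 15 mg and 60 mg with one count per subject, and the resulting tables could not show whether incidence or severity differs between doses.

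The Period 1 definition is a firmer defect, because every TEAE that starts after the Period 2 dose satisfies both definitions on their plain wording.

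The percentages above rest on assumed counts. They show what information is lost and do not predict AE rates in this study. No primary or PK analysis is affected. Even with split tables, dose is confounded with period because the order is fixed, so any difference between doses is descriptive.

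**What to change.** Amend SAP section 4.11.1 and the table shells:

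- Present the TEAE overview, SOC/PT, severity, relationship and serious-TEAE tables by cohort and by period (dose) of onset, with a both-doses column and an overall column.
- Apply the once-per-subject and worst-grade rules within each period, and across both periods in the both-doses column.
- Use the subjects dosed in that period as the denominator.
- Define a Period 1 TEAE as one starting at or after the Period 1 dose and before the Period 2 dose. SAP section 4.10 already closes the window this way for concomitant medications.
- State that the comparison between doses is descriptive because dose and period coincide.

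The dose-level rule in protocol section 9.4 already permits this, so no protocol change is needed. No new data are collected. The cost is wording, some programming, and wider tables with small counts.

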## 9.4.3. Other Analyses

#### 9.4.3.1. Pharmacokinetic Analyses

Individual ALXN1840 PK, assessed as plasma total Mo concentration-time data will be listed, plotted, and summarized with descriptive statistics, with mean PK data plotted. The following plasma total Mo PK parameters will be derived for individual subjects and summarized with descriptive statistics:  $C_{max}$  in plasma, time to maximum concentration  $(t_{max})$  in plasma, area under the plasma concentration versus time curve from time 0 to the last quantifiable concentration  $(AUC_t)$ , area under the plasma concentration versus time curve from time 0 (dosing) to infinity  $(AUC_{\infty})$ , apparent terminal-phase  $\lambda_z$ ,  $t_{1/2}$ , CL/F, apparent volume of distribution  $(V_d/F)$ , and relative bioavailability  $(F_{rel})$  in Japanese versus non-Japanese subjects. Analyses of other PK data including, but not limited to those, of PUF Mo may be conducted. PK parameters will be calculated using Phoenix WinNonlin versus time total Mo concentration versus time of the last quantification ( $V_d/F$ ), and relative bioavailability ( $F_{rel}$ ) in Japanese versus non-Japanese subjects. Analyses of other PK data including, but not limited to those, of PUF Mo may be conducted. PK parameters will be calculated using Phoenix WinNonlin versus time total Mo concentration versus time and versus time curve from time 0 ( $V_d/F$ ), and  $V_d/F$  ( $V_d/F$ ) and  $V_d/F$  ( $V_d/F$ ) and  $V_d/F$  ( $V_d/F$ ) are versus time curve from time 0 ( $V_d/F$ ).

Detailed PK analyses will be described in the PK/PD data analysis plan (DAP), which will be finalized before database lock.

## 9.4.3.1.1. Pharmacokinetic Analysis for Ethnic Difference

The PK parameters for total Mo ( $C_{max}$ ,  $AUC_t$ , and  $AUC_{\infty}$ ) will be evaluated for Japanese and non-Japanese cohorts, using an analysis of variance (ANOVA) statistical model with cohort and dose as the fixed effects, and subject as a random effect, using the natural logarithms of the data. The within-subject CV for the  $C_{max}$ ,  $AUC_t$ , and  $AUC_{\infty}$  will be estimated using the mean squared error from the ANOVA. In addition, the Japanese versus non-Japanese cohorts will be evaluated using descriptive statistics: for each cohort, the geometric means and the associated 95% confidence intervals of  $C_{max}$ ,  $AUC_t$ , and  $AUC_{\infty}$  will be reported at each dose.

Detailed PK analyses will be described in the PK/PD DAP finalized before database lock.

#### 9.4.3.1.2. Pharmacodynamic and Biomarker Analyses

Individual ALXN1840 PD and biomarkers, assessed as plasma total Cu (PD), NCC (PD), NCCcorrected (PD), Cp (biomarker), and CpC (biomarker) concentration-time data will be listed and summarized with descriptive statistics and plotted. The same analyses will be conducted on the absolute and percent changes from baseline of these PD and biomarker concentration-time data. Analyses of other biomarker data including, but not limited to, those of PUF Cu may be conducted.

Detailed PD analyses will be described in the PK/PD DAP finalized before database lock.

## 9.4.3.1.3. Exploratory Analyses

Dose-proportionality of ALXN1840 PK between the 15 mg and 60 mg doses within each cohort and with combined cohort data will be assessed via graphical display and evaluated quantitatively via dose-normalized  $C_{\text{max}}$  and AUC values.

Relationships between CL/F and body size (body weight [kg] and BMI [kg/m²]) will be evaluated graphically for the Japanese and non-Japanese cohorts and with combined cohort data. If suggested by the graphs, regression models may be fit to the data.

Detailed exploratory analyses will be described in the PK/PD DAP finalized before database lock.

## 9.5. Interim Analyses

No interim analyses are planned for this study.

# 10. SUPPORTING DOCUMENTATION AND OPERATIONAL CONSIDERATIONS

# 10.1. Appendix 1: Regulatory, Ethical, and Study Oversight Considerations

## 10.1.1. Regulatory and Ethical Considerations

- This study will be conducted in accordance with the protocol and with the following:
  - Consensus ethical principles derived from international guidelines including the Declaration of Helsinki and Council for International Organizations of Medical Sciences International Ethical Guidelines
  - Applicable ICH of Technical Requirements for Pharmaceuticals for Human Use GCP Guidelines
  - Applicable Japan Ministry of Health, Labour and Welfare guidance on Basic Principles on Global Clinical Trials
  - Applicable laws and regulations
- The protocol, protocol amendments, ICF, IB, and other relevant documents (eg, advertisements) must be submitted to an IRB/IEC by the investigator and reviewed and approved by the IRB/IEC before the study is initiated.
- Any amendments to the protocol will require IRB/IEC approval before implementation of changes made to the study design, except for changes necessary to eliminate an immediate hazard to study subjects.
- The investigator will be responsible for the following:
  - Providing written summaries of the status of the study to the IRB/IEC annually or more frequently in accordance with the requirements, policies, and procedures established by the IRB/IEC
  - Notifying the IRB/IEC of SAEs or other significant safety findings as required by IRB/IEC procedures
  - Providing oversight of the conduct of the study at the site and adherence to requirements of 21 CFR, ICH guidelines, the IRB/IEC, European regulation 536/2014 for clinical studies (if applicable), and all other applicable local regulations

#### 10.1.2. Financial Disclosure

Investigators and sub-investigators will provide the Sponsor with sufficient, accurate financial information as requested to allow the Sponsor to submit complete and accurate financial certification or disclosure statements to the appropriate regulatory authorities. Investigators are responsible for providing information on financial interests during the course of the study and for 1 year after completion of the study.

#### 10.1.3. Informed Consent Process

• The Investigator or his/her representative will explain the nature of the study to the subject or his/her legally authorized representative and answer all questions regarding the study.

- Subjects must be informed that their participation is voluntary. Subjects or their legally authorized representative will be required to sign a statement of informed consent that meets the requirements of 21 CFR 50, local regulations, ICH guidelines, Health Insurance Portability and Accountability Act (HIPAA) requirements, where applicable, and the IRB/IEC or study center.
- The medical record must include a statement that written informed consent was obtained before the subject was enrolled in the study and the date the written consent was obtained. The authorized person obtaining the informed consent must also sign the ICF.
- Subjects must be re-consented to the most current version of the ICF(s) during their participation in the study.
- A copy of the ICF(s) must be provided to the subject or the subject's legally authorized representative. The Investigator must retain the original version of the signed ICF(s).

